#### 10.3 Variables

Variables (primary and secondary) are specified in Section 9.4.

#### 10.4 Statistical and analytical plans

#### 10.4.1 Demographic and other baseline characteristics

Summary statistics (arithmetic mean, standard deviation, median, minimum and maximum for quantitative variables) will be presented by treatment arm. Frequency tables for qualitative data will be provided. Medical history findings will be summarized using MedDRA (Medical Dictionary for Regulatory Activities) terms.

#### 10.4.2 Maximum tolerated dose

Individual listings and treatment summaries of dose limiting toxicities with CTCAE v4.03 code and grade will be presented.

The incidence of subjects with DLTs during Cycle 1 will be summarized by treatment and, as possible, modeled as a function of BAY 1163877 dose using Bayesian logistic regression. The moderately-informative independent priors used during the interim analysis (see Section 16.4 for details) as well as non-informative priors will be used for this analysis in order to assess sensitivity of the estimates. Parameter estimates and model predictions will be reported with 90% credibility sets. The MTD will be computed as a derived function of model parameters as:

 $MTD = (\log(0.2/0.8) - \text{intercept}) / \text{slope}.$ 

The posterior distribution of the MTD will be summarized in tabular and graphical formats.

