#### Methodology

Eligible cancer subjects will be enrolled at multiple centers worldwide. In total, the "on study" period for the subjects comprises 3 phases:

- Pre-treatment
- FGFR expression / FGFR mutation testing
- Screening
- Treatment

Study Part 1 / dose escalation + MTD expansion (all comer):

Individual number of 21-day Cycles with BAY 1163877 monotherapy (tablet or solution) until disease progression or as long as clinical benefit is assumed by the investigator or until unacceptable toxicity occurs.

Study Part 1 /"tablet bridging cohort" (all comer):

In one of the dose escalation cohorts, administration of a single dose of BAY 1163877 using the tablet formulation on Cycle 1, Day -3 followed by solution formulation starting Cycle 1, Day 1 as described above.

Study Part 2 / MTD expansion (sqNSCLC + LAC + BC + SCCHN):

Individual number of 21-day Cycles with continuous BAY 1163877 monotherapy (tablet or solution) until disease progression or as long as clinical benefit is assumed by the investigator or until unacceptable toxicity occurs.

Study Part 3 / MTD expansion "Safety cohort" (sqNSCLC + LAC + BC):

Individual number of 21-day Cycles with continuous BAY 1163877 monotherapy (tablet) until disease progression or as long as clinical benefit is assumed by the investigator or until unacceptable toxicity occurs. 12

<sup>12 Part 3 added by Amendment 7, see section 15.6.2.2

No. BAY 1163877 / 16443

17 Oct 2018 Version 8.0 Page: 13 of 395

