#### Targeted / planned enrollment:

- Study Part 1 / dose escalation (all comer): The total number of subjects will depend on the number of cohorts necessary to identify the MTD. Relative bioavailability of the tablet formulation in comparison to the solution formulation will be performed in all subjects enrolled in one of the dose escalation cohorts; pharmacokinetic data are needed in a minimum of 3 subjects for relative bioavailability assessment.
- Study Part 1 / MTD expansion (all comer): Additional subjects will be enrolled to have 20 evaluable "all comer" subjects treated at MTD.
- Study Part 2 / MTD expansion (sqNSCLC + LAC + BC + SCCHN): additional subjects will be enrolled to have 20 evaluable subjects with sqNSCLC or LAC and at least 30, up to a maximum of 50 evaluable subjects with BC and at least 8 subjects with SCCHN treated at MTD. 
- Study Part 3 / MTD expansion "Safety cohort" (sqNSCLC + LAC + BC): additional subjects will be enrolled to have approximately 20 subjects with sqNSCLC or LAC and approximately 20 subjects with BC treated at MTD.

PK assessments will be performed in all subjects participating in study Part 1 / dose escalation and MTD expansion (all comer) and study Part 3/ MTD expansion "Safety cohort". Additionally, PK assessments are planned in at least 12 subjects participating in study Part 2 / MTD expansion (sqNSCLC + LAC + BC + SCCHN) such that valid PK data are available in 8 subjects and in approximately 8 subjects of the MTD expansion cohorts with impaired renal function at baseline. Food effect PK assessment is planned in approximately 8 subjects enrolled in the MTD expansion cohorts (study Part 1 and Part 2). Subjects participating in "food effect assessment" in study Part 2 may be included in the total sample size of 12 if all protocol requirements are met.

All subjects participating in either of the 3 MTD expansion cohorts (Part 1, Part 2 and Part 3 despite subjects with impaired renal function) will have 2 PK samples drawn for the purpose of exposure-response modelling on Day 1 of Cycles 2, 3, 4, and 5 (1 blood sample just before the morning dose of BAY 1163877 and 1 blood sample between 0.5 and 1.5 hours post-dose). Subjects in Part 3 will provide one PK sample within 1 hour of biopsy collection in Cycle 2. The dose needs to be taken under supervision and the time

 Part 3 - Safety cohort - was added by Amendment 7, see section 15.6.2.6

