When a subject starts new anti-cancer therapy, he / she is no longer considered "on study". An End of Treatment (EOT) visit will be performed for all subjects within 0-14 days after

<sup>32 Part 3 - Safety cohort - was added by Amendment 7, see section 15.6.2.6

17 Oct 2018 Version 8.0 Page: 40 of 395

administration of the last dose of BAY 1163877. The Follow-up visit for subjects who either discontinue prematurely or finish dosing with BAY 1163877 will be performed 30-35 days after the last study drug treatment. There will be no long-term (survival) follow-up (FU) period.

Treatment: Subjects with PK assessment (all subjects of study Part 1 and 3 and at least 12 subjects of study Part 2 and approximately 8 subjects of the MTD expansion cohorts with impaired renal function at baseline) will receive BAY 1163877 (tablet or solution) on a continuous schedule starting with single-dose administration on Cycle 1, Day 1, followed by a "drug-free day" (to enable single dose PK assessments, except for subjects in Part 3 who will receive BAY 1163877 twice daily continuously with no "drug free day"). Treatment with BAY 1163877 will resume on Day 3 of Cycle 1 if no protocoldefined dose-limiting toxicities (DLTs) are reported. Starting on Cycle 1, Day 3, the study drug will be self-administered twice daily for the remaining 19 days of Cycle 1. For subsequent cycles, study drug will be administered twice daily for 21 days until disease progression or as long as clinical benefit is assumed by the investigator or until unacceptable toxicity occurs.

In one of the dose escalation cohorts in study Part 1 ("tablet bridging cohort"), relative bioavailability of the tablet formulation will be assessed by administration of a single dose of the tablet formulation on Cycle 1, Day -3. Starting with Cycle 1, Day 1, subjects enrolled in the "tablet bridging cohort" will continue with the solution formulation as described above. Depending on the results from the relative bioavailability assessment, subjects who initially start with solution formulation may be switched to tablet formulation in later cycles.

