#### **Determination of the maximum tolerated dose (MTD)**

An adaptive dose escalation design will be used to determine the MTD in study Part 1 (all

.

<sup>33 Part 3 was added by Amendment 7, see section 15.6.2.6

17 Oct 2018 Version 8.0 Page: 41 of 395

comer). The MTD is defined as the highest dose that can be given such that not more than 20% of subjects experience a DLT during Cycle 1.

Without the occurrence of toxicities, dose escalation could be stopped and RP2D may be determined based on PK and/or PD results. The decision to continue treatment for an individual subjects will be made by the investigator according to the criteria specified in the protocol (Section 8.4).

Each cohort will be evaluated after all subjects have completed the first 21 days of treatment (which will subsequently referred to as "Cycle 1") or early discontinued.

[figure not shown]
Safety monitoring will occur by telephone conferences with participation of the investigators and the sponsor on a regular basis.

At the time of dose escalation the available clinical safety information is discussed in a telephone conference by the involved investigators and representatives from the Sponsor including the Study Medical Expert as well as representatives of other clinical and if required further contributing functions (drug safety monitoring team – DSMT). During this telephone conference it will be judged if dose escalation can proceed as planned according to the procedure outlined below. Dose escalation for subsequent cohorts will only be considered after full evaluation of at least Cycle 1 safety data from the previous cohort.

The National Cancer Institute (NCI) Common Terminology Criteria for Adverse Events Version 4.03 (CTCAE v4.03) will be used to grade toxicities / adverse events. In general, the assessment of relationship between adverse events (AEs) and BAY 1163877 will be performed as described in Section 9.5.1.2.3.

The dose escalation will be performed as follows:

- Initially 3 subjects per dose level will be enrolled. In case 2 or more sites are conducting the dose escalation part, the initial enrolment of 4 subjects per dose level is optional.
- The starting dose of BAY 1163877 is 50 mg given as a single dose on Cycle 1, Day 1, and twice daily (b.i.d.) from Cycle 1, Day 3 (100 mg / day).
- The maximum dose escalation will be 2-fold.
- Possible daily doses of BAY 1163877 starting from 100mg in increments of 100mg.

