## 8.4.2.1 Dosing schedule - amended

BAY 1163877 will be given in cycles. Each cycle lasts 21 days. There will be no break between treatment cycles.

Subjects will receive either the solution (IMP 1) or the tablet (IMP 2) formulation of BAY 1163877, except for subjects in the "tablet bridging cohort" who will receive both a single dose using the tablet formulation and multiple doses using the solution formulation.

Study Part 1 / dose escalation + MTD expansion cohort (all comer):

Cycle 1 Day -3 ("tablet bridging cohort" only): Single-dose administration of

BAY 1163877 tablet formulation on Cycle 1, Day -3; thereafter continuation with solution formulation starting on Cycle 1, Day 1 (see dosing schedule

below)

Cycle 1: Single-dose administration of BAY 1163877 on

Cycle 1, Day 1 (in the morning)

No administration of BAY 1163877 on Cycle 1,

Day 2 ("drug-free day")

Twice daily administration of BAY 1163877 on

Days 3-21

Cycle 2 and subsequent cycles: Twice daily administration of BAY 1163877 on

Days 1-21.

Study Part 2 / dose expansion (sqNSCLC + LAC + BC + SCCHN):

- Subjects participating in PK assessments will follow the dosing regimen specified for study Part 1.
- Subjects without PK assessment will receive BAY 1163877 twice daily from Cycle 1, Day 1 ongoing.

Study Part 1 (MTD expansion cohort) or Study Part 2 / "Food Effect Assessment": Approximately 8 subjects will receive single doses of BAY 1163877 on Cycle 1, Day -3 (after consumption of a high-fat, high-calorie breakfast) and on Cycle 1, Day 1 (after an overnight fast of at least 8 hours). BAY 1163877 will not be administered on Cycle 1, Day -2 and Day -1, in the evening of Cycle 1, Day 1 and on Cycle 1, Day 2.

[figure not shown]
Study Part 3 / MTD expansion "Safety cohort" (sqNSCLC + LAC + BC):

• Subjects will receive BAY 1163877 twice daily from Cycle 1, Day 1 ongoing.

-

<sup>48 Part 3 added by Amendment 7, see section 15.6.2.14

<sup>49 Part 3 - Safety cohort - was added by Amendment 7, see section 15.6.2.15

17 Oct 2018 Version 8.0 Page: 60 of 395

Evidence of tumor progression, unacceptable toxicity, consent withdrawal or subject's withdrawal from the study at the discretion of the Investigator may lead to termination of treatment (see Section 7.2.1).

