#### 10.2 Analysis sets

All subjects who received at least one dose of the study medication will be included in the safety evaluation. All subjects who completed Cycle 1 or discontinued during Cycle 1 due to an adverse event or DLT will be included in the MTD evaluation. All subjects who have received at least one dose of BAY 1163877 and who have post-baseline efficacy data available will be included in the efficacy evaluations.

All subjects with valid pharmacokinetic data will be included in the evaluation of pharmacokinetic concentrations and parameters.

Subjects to be included in the relative bioavailability evaluation ("tablet bridging cohort") should have evaluable pharmacokinetic data on both Cycle 1, Day -3 and Cycle 1, Day 1.

No. BAY 1163877 / 16443

17 Oct 2018 Version 8.0 Page: 105 of 395

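### The DLT model pools solution and tablet on nominal mg, so the single reported MTD may not carry the 20% DLT rate for the tablet if the two formulations differ in exposure

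*Protocol*

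**What the plan says.** **Model and estimator.** Section 10.4.2 has the incidence of Cycle 1 DLTs "modeled as a function of BAY 1163877 dose using Bayesian logistic regression". It continues: "The MTD will be computed as a derived function of model parameters as" (log(0.2/0.8) - intercept) / slope. Dose is the only predictor. The target, from Section 6, is the highest dose at which "not more than 20% of subjects experience a DLT during Cycle 1".

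**Who enters.** Section 10.2 takes subjects who completed Cycle 1, and those who "discontinued during Cycle 1 due to an adverse event or DLT will be included in the MTD evaluation". It does not separate formulations.

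**What subjects take.** Section 8.4.2.1: "Subjects will receive either the solution (IMP 1) or the tablet (IMP 2) formulation of BAY 1163877", with the tablet bridging cohort taking one tablet dose and then solution. Section 6 allows tablet or solution in Part 1 (escalation and expansion) and in Part 2. For Part 3 the Synopsis (Methodology) gives "Individual number of 21-day Cycles with continuous BAY 1163877 monotherapy (tablet) until disease progression". Section 8.1 treats Parts 2 and 3 at the MTD determined in Part 1 and mentions no conversion.

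**What is known about the tablet.** Section 4 makes its bioavailability relative to solution a secondary objective. Section 6 assesses this in one escalation cohort and says "pharmacokinetic data are needed in a minimum of 3 subjects for relative bioavailability assessment". Section 10.4.5 reports the ratio with exploratory 90% confidence intervals and sets no acceptance range. Section 6 adds: "Depending on the results from the relative bioavailability assessment, subjects who initially start with solution formulation may be switched to tablet formulation in later cycles".

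**The concern.** The trial's primary outcome is one mg figure tied to a 20% Cycle 1 DLT rate. That figure has the same meaning for both formulations only if equal mg gives about equal exposure. The protocol does not assume this; it sets out to measure it. Yet Section 10.4.2 pools DLTs from both formulations on the nominal mg scale, and no stated step carries the measured ratio into the MTD estimate.

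If the ratio is not near 1, the fitted slope and the derived MTD describe a mixture whose composition depends on how many subjects happened to start on each formulation. The rationale for Amendment 1 (Section 15.1.1) plans the move to tablet after the bridging assessment. If that order was followed, formulation would also be partly confounded with dose. The tablet is always used in Part 3 and may be used in Parts 1 and 2, so it is the formulation for which the 20% label matters most.

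**Working it through.** The protocol states no CV, acceptance range or precision target for the tablet/solution comparison, so there is no figure of its own to reproduce. Two checks show the scale. Both rest on assumed inputs.

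**1. How well the within-subject comparison can fix the ratio.**

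Inputs: n = 3, the minimum in Section 6; ANOVA on logs with subject and formulation effects (Section 10.4.5), which leaves n - 1 = 2 degrees of freedom; within-subject CV assumed, because none is given.

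Formula, for a true ratio of 1: 90% limits = exp(± t(0.95, n-1) × s × sqrt(2/n)), with s = sqrt(ln(1 + CV²)).

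At CV 30%: s = 0.294, t = 2.920, sqrt(2/3) = 0.816. The half-width is 0.700 on the log scale, so the limits are 0.50 to 2.01.

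| Assumed CV | n = 3 | n = 4 | n = 9 |
|---|---|---|---|
| 20% | 0.62-1.60 | 0.72-1.39 | 0.84-1.19 |
| 30% | 0.50-2.01 | 0.61-1.63 | 0.77-1.29 |

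With three subjects, a ratio of 0.8 or 1.25 cannot be told from 1. In the bridging cohort the tablet dose also always comes first (Day -3) and the solution second (Day 1), so formulation and period cannot be separated.

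**2. What a ratio other than 1 does to the DLT rate.**

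The MTD formula in Section 10.4.2, as printed, is linear in dose. Let a = logit(DLT rate at dose 0), which is assumed, and let r be tablet exposure divided by solution exposure. If the 20% dose was estimated on solution, the tablet's DLT rate at the same mg is expit(a + r × (logit(0.2) - a)), with logit(0.2) = -1.386.

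Worked case, 1% at dose 0: a = -4.595 and logit(0.2) - a = 3.209. At r = 1.25 the logit is -4.595 + 4.011 = -0.584, or 36%. At r = 0.8 it is -4.595 + 2.567 = -2.028, or 12%.

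| Assumed DLT rate at dose 0 | r = 0.8 | r = 1 | r = 1.25 |
|---|---|---|---|
| 1% | 12% | 20% | 36% |
| 2% | 13% | 20% | 32% |
| 5% | 15% | 20% | 27% |

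The result does not depend much on the dose scale. With a logistic model in log dose and an assumed slope of 2 to 3, expit(ln 0.25 + slope × ln r) gives 28-33% at r = 1.25 and 11-14% at r = 0.8.

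This is the unmixed case, with all the information on the MTD coming from solution. Where tablet subjects contribute DLT data near the MTD, the gap is smaller, but the reported figure is then a blend.

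**The case against.** Most of the case on the other side is fair, and it limits how far the point can go.

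- **Three is a minimum.** Section 6 makes the bridging comparison in all subjects of one escalation cohort. Cycle 1 PK is also taken in all Part 1 subjects, in at least 12 Part 2 subjects and, on Day 15, in all of Part 3 (about 20 + 20 = 40 subjects; Sections 6 and 9.4.2.1). A reader might infer that tablet exposure is known only from three subjects. The protocol does not support that. What stands is that the only planned formal tablet/solution comparison may be that small.
- **PK is not ignored.** Section 8.4.1 uses PK, if available, in each dose step. Section 10.5 allows PK/PD modeling of DLT rates. Section 6 uses PK for the recommended Phase II dose, and Section 10.6 plans exposure-response modeling. It would therefore be wrong to say that exposure plays no part in dose decisions. But the modeling in Section 10.5 is optional and serves interim dose selection, and none of these steps changes the MTD estimator in Section 10.4.2.
- **The later switch.** Moving subjects to tablet in later cycles does not affect Cycle 1 DLTs. The mixing comes only from the formulation taken in Cycle 1, and the protocol does not say how many subjects start on tablet.
- **Part 2 is not tablet only.** Only Part 3 is.
- **Partly self-correcting.** Read literally, Section 10.2 admits expansion subjects to the MTD evaluation, so tablet DLTs at the MTD would enter the final fit. That helps, but the output is still one unlabelled mg figure.
- **SAP detail.** A table split or an additional sensitivity analysis could normally wait for the SAP. Here the protocol itself fixes a two-parameter estimator on nominal dose, so the choice is open to comment. Section 16.4, which holds the model details, was not available for checking.

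**Conclusion.** The point holds as a limitation of a fixed estimator. Section 10.4.2 pools two formulations on nominal mg while their exposure ratio is still an open question, and the resulting MTD is used unconverted in tablet-only Part 3. If the ratio is near 1, nothing is lost. At ratio 1.25 the tablet's DLT rate could be about 7 to 16 points above the 20% target; at ratio 0.8 it could be about 5 to 8 points below. These figures assume a model linear in dose, a DLT rate of 1-5% at dose 0 and an MTD estimated on solution.

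A reader might infer that the expansion cohorts are dosed at a level whose DLT rate is known to differ from 20%. The protocol does not show that. It reports no ratio, no CV and no dose-DLT slope, and making bioavailability an objective does not mean that the formulations differ. Direction and size are unknown. This is a worthwhile and cheap improvement to the analysis; it does not show that the MTD is wrong.

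**What to change.** In Section 10.4.2:

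1. Tabulate Cycle 1 DLTs by dose and by the formulation with which the subject starts repeated dosing in Cycle 1. Bridging-cohort subjects count as solution, which they take from Day 1.
2. Add one sensitivity refit of the existing Bayesian logistic model. Either multiply tablet doses by the estimated tablet/solution AUC ratio, or replace dose by observed exposure. Take the ratio from the bridging comparison, supported by the dose-normalised Cycle 1 PK already collected in all Part 1 subjects. The dose-normalised part assumes approximate dose proportionality, which Section 10.4.5 already examines. Refitting at both 90% limits of a three-subject ratio is not advised: at CV 30% it would rescale tablet doses by 0.50 to 2.01 and say almost nothing.
3. State the formulation to which the reported MTD refers, so that Sections 8.1, 8.4.2.1 and 10.4.2 agree on it.

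The cost is one table and one extra model fit, with no new subjects or samples. The downside is a possibly wider reported uncertainty for the MTD. No dose or clinical rule is proposed.

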#### 10.4.3 Adverse events

Individual listings of adverse events will be provided. The incidence of treatment-emergent adverse events (TEAEs) and treatment-emergent drug-related adverse events (TEADRs), respectively, will be summarized by cohort in frequency tables using worst CTCAE v4.03 grade. Frequency tables will also be provided for the changes of worst CTCAE v4.03 grade after start of treatment versus baseline. In addition analysis will be done using MedDRA terms.

#### **10.4.4 Safety parameters**

Quantitative data (vital signs, ECG) will be described by the following summary statistics: arithmetic mean, standard deviation, median, minimum and maximum. These summary statistics will be presented by cohort for the original data as well as for the difference to baseline. Frequency tables will be provided for qualitative data.

Laboratory data outside the reference range will be listed with abnormal values flagged. The incidence of laboratory data outside the reference range (low, high) will be summarized by cohort in frequency tables. The incidence of laboratory toxicities will be summarized by worst CTCAE v4.03 grade and by cohort. Frequency tables will be

17 Oct 2018 Version 8.0 Page: 106 of 395

provided for the changes of worst CTCAE v4.03 grade after start of treatment versus baseline.

#### 10.4.5 Pharmacokinetic data

The concentration-times courses of all analytes will be tabulated for each cohort. The following statistics will be calculated for each of the sampling points: arithmetic mean, standard deviation and coefficient of variation (CV), geometric mean, geometric standard deviation (re-transformed standard deviation of the logarithms) and CV, minimum, median, maximum value and the number of measurements. Means at any time will only be calculated if at least 2/3 of the individual data were measured and were above the lower limit of quantification (LLOQ). For the calculation of the mean value a data point below LLOQ will be substituted by one half of this limit. In tables showing mean values, where values below LLOQ are included in the calculation of mean values, these means will be marked.

Individual and geometric mean concentration vs. time curves of all analytes (using the actual sampling times for individual plots and the planned sampling times for mean plots) will be plotted by treatment using both linear and semilogarithmic scale. The amount and percent of drug excreted into urine will be graphically illustrated for the sampling interval as well as for the whole sampling period (bar-charts for the individual data and the arithmetic mean including standard deviation).

Pharmacokinetic characteristics ( $t_{max}$  and  $t_{last}$  excluded) will be summarized by the statistics mentioned above.  $t_{max}$  and  $t_{last}$  will be described utilizing minimum, maximum and median as well as frequency counts. Amount and percent of drug excreted in urine will be described by arithmetic statistics, minimum, maximum and median.

To investigate dose proportionality, an explorative analysis of variance (ANOVA), including the factor cohort, will be performed on the log-transformed values of appropriate PK parameters calculated from single (where applicable) and multiple dose PK profiles.

In order to evaluate the relative bioavailability of the tablet formulation, tablet  $C_{max}/D$ ,  $AUC(0-t_{last})/D$  and AUC/D on Cycle 1, Day -3 will be compared to solution  $C_{max}/D$ ,  $AUC(0-t_{last})/D$ , AUC/D on Cycle 1, Day 1 for all analytes. If needed, additional PK parameters may be used for relative bioavailability assessment. The logarithms of these PK parameters will be analyzed using analysis of variance (ANOVA) including subject and formulation effects. Based on these analyses, point estimates (LS-means) and exploratory 90% confidence intervals for the ratios (tablet/solution) of  $C_{max}/D$ ,  $AUC(0-t_{last})/D$ , AUC/D will be calculated by retransformation of the logarithmic data using the intra-individual standard deviation of the ANOVA.

In order to evaluate the food effect, BAY 1163877  $C_{max}$  and AUC(0- $t_{last}$ ) on Cycle 1, Day -3 and  $C_{max}$  and AUC(0- $t_{last}$ ) on Cycle 1, Day 1 will be compared. The logarithms of  $C_{max}$  and AUC(0- $t_{last}$ ) will be analyzed using ANOVA including subject and food effects. Based on these analyses, point estimates (LS-means) and exploratory 90% confidence intervals for the ratios (high-fat, high-calorie meal / fasting) of  $C_{max}$  and AUC(0- $t_{last}$ ) will be calculated by retransformation of the logarithmic data using the intra-individual

17 Oct 2018 Version 8.0 Page: 107 of 395

standard deviation of the ANOVA.

